Using this approach, it is expected to address the informatics challenge of determining how to design information technology that improves engagement and clinical outcomes for patients who require continuous monitoring and who engage an informal caregiver in self-management outside clinical settings. Our work extends the design of remote-monitoring systems from stationary, home-based systems to wearable devices that patients can engage with throughout an active day in the community. Our research team—which consists in a biomedical systems engineer, a human factors engineer specialized in consumer health informatics, a pediatric endocrinologist, and a pediatrician specialized in clinical research — works in alliance with the Center for Diabetes Technology at the University of Virginia. Study team members have developed this ambulatory platform that will be used as the foundation for this study.

Rationale: The hypothesis of this study is that individuals randomized to the CGM/Fitbit with no weekly feedback (Control Group) will improve management modestly initially (as a result of either of new access to CGM or the Hawthorne effect of being studied), but their measures of engagement (patient self-management behavior (i.e. personal insulin parameters) and diabetes-related dyad communication) will return to baseline levels by the 12-week evaluation. By contrast, it is hypothesize that individuals randomized to CloudConnect (Experimental Group) will have a greater increase in engagement and dyad communication by 8 weeks that is sustained by 12 weeks (3 months).

It is further hypothesize that adolescents randomized to CloudConnect will have a lowering of HbA1c that is related to the increase in dyad disease-specific engagement. Moreover, our hypotheses are that this unique self-management approach in T1D will increase engagement of adolescents and their informal caregiver through increased communication and self-management behavior, and that this increase in engagement will lead to improved medical outcomes.

These hypotheses are based on data from preliminary studies collected by the study group and the literature. This preliminary data support that parents of adolescents with T1D are eager to follow their child's blood

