This is a randomized control, open-label, single-site clinical trial. We will target completion by eighty adolescents (age 12-17 years) with Type 1 diabetes and their parent/guardian (age 18+) to participate in a 3 month outpatient study. Participants will be randomized to either a Control Group or Experimental Group. Both groups will use the study continuous glucose monitor, study activity tracker, and a study insulin pen if an multiple daily injection (MDI) user. Subjects who use an insulin pump to treat their type 1 diabetes will use their personal insulin pump. All subjects will be asked to download this equipment and provide it to the study team each week. The study team will communicate weekly with each group. Questionnaires will also be completed at the beginning and at the end of the study. The Experimental Group will receive the CloudConnect Reports. The Control Group will not receive this feedback.

3. Does the study involve a placebo?

No

Human Participants

Ages: 12-17 years old and at least one of parent(s)/guardian(s) (age 18+)/guardian (adolescent/parent dyad is required for participation in this trial)

Sex: Male and Female

Race: All

1. Provide target # of subjects (at all sites) needed to complete protocol.

For the Pilot Study, up to 6 adolescents and 6 parent(s)/guardian(s) may complete the study. These pilot subjects may also participate in the Main Study.

For the Main Study, 160 subjects (80 dyads – consisting of 80 adolescents and 80 adults) need to complete the study.

2. Describe expected rate of screen failure/ dropouts/withdrawals from all sites.

We expect that because the length of the study it could be 20-30% dropouts/withdrawals from the study.

3. How many subjects will be enrolled at all sites?

This is a single site clinical trial to be completed at UVa.

4. How many subjects will sign a consent form under this UVa protocol?

Up to 210 subjects (105 dyads – consisting of 105 adolescents and 105 parent(s)/guardian(s)) will sign consent for the Main Study and up to 16 subjects (8 parent/child dyads) will sign a consent for the Pilot Study. i.e. total = 226 (210+16)

Inclusion/Exclusion Criteria

1. List the criteria for inclusion for Pilot and Main Study Adolescent Subjects

- Willingness to provide informed consent
- Adolescents ages ≥ 12 and ≤ 17 years old with a parent/guardian (18+ yo) who is willing to participate with the child

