Use of anti-diabetic agents other than short-acting insulin for CSII subjects or long-acting insulin for MDI subjects, including: metformin, sulfonylureas, meglitinides, thiazolidinediones, dipeptidyl peptidase 4 (DPP-4) inhibitors, glucagon-like peptide 1 agonists and alpha-glucosidase inhibitors

Statistical Considerations

1. Is stratification/randomization involved? Yes

► IF YES, describe the stratification/ randomization scheme.

During the main study, up to 210 adolescents, ages 12 years - 17 years (inclusive), will be recruited with one of their parent(s)/guardian(s), 18+ y.o., in each arm. Based on experience, approximately 40 adolescents & 40 parent(s)/guardian(s) in each arm will complete the study (N=80 adolescents and 80 parents, total 160 subjects). Male and female adolescents will be recruited, and all racial/ethnic groups will be eligible for participation. Participants will be recruited in randomization blocks of 4. The goal is to target a minimum of 10 participants in each of the 4 stratification subgroups based on age (12-14 y.o and 15-17 y.o.) and insulin therapy (CSII and insulin pen). ,

► IF YES, who will generate the randomization scheme?

Sponsor
 UVa Statistician. Answer/Response:
 UVa Investigational Drug Service (IDS)
 Other: Center for Diabetes Technology (CDT) personnel

2. What are the statistical considerations for the protocol?

The objectives section and the statistical section should correspond, and any objective for which analysis is unfeasible should be deleted. Also, the estimates and non-statistical assumptions of the statistical section should be supported by discussion in the background section.

The answer to this question should include:

-Study Design/Endpoints

- Recap of study objectives and endpoint definitions. An assessment of how study objectives will be assessed by identifying & defining which endpoints will be used to assess each component of the study objectives.
- The study design should include contingencies for early stopping, interim analyses, stratification factors (If applicable), and any characteristics to be incorporated in analyses.
- The power/precision of the study to address the major study endpoint(s), the assumptions involved in the determination of power/precision.

Study Design:

This study employs a randomized design in which one group of participants will be assigned to use the CloudConnect system and the other group to CGM using their insulin paramenters and treatments.

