Visit 2 (may be combined with Visit 1, may be done via phone or video): Adolescent subjects will be randomized and trained on the use of the study CGM and Fitbit. The CGM will be inserted into their abdomen per manufacturer instructions. Both Control and Experimental Group subjects will use their own personal pump. If the subject uses multiple daily injections (MDI), a commercially available Bluetooth connected insulin pen (inPen) will be given to both the Control and Experimental subjects in order to be able to collect the data accurately about meal time bolus treatments. Both pump users and MDI subjects will use their personal insulin. Each group will provide the study team weekly downloads from the study equipment and the personal insulin pump. Weekly CloudConnect reports will be provided to the Experimental Group participants *only*.

Depending on the subjects/family preference, the study team contact subjects via phone calls, text messages and/or emails at least once a week during the trial to:

- a) Remind them to download and transmit the data
- b) Check for AEs or SAEs
- c) Ask weekly standardized questions

All subjects will be reminded on how to download study data, if necessary. Both groups may complete a 1-week run-in period if they are CGM-naïve to ensure they are comfortable with the use of the study equipment, that all the study devices work properly, and to address issues related to transmission of the data to the study team. This run-in period may be repeated as necessary up to 3 times at the request of the study subject or study team. This data will not be included as part of the 12 week data collection. For subjects who have CGM experience, the investigator will determine if it is appropriate for he or she to skip the run-in period.

Visit 3 Check-in (Week 8 / on-site, email, or phone):

Subjects will download diabetes equipment weekly and submit the data to the study team for 12 weeks. Subjects may be asked to repeat a week of data collection if the quality of the data is insufficient for analysis.

A Check-In with the adolescent and parent/guardian will be completed to evaluate compliance and to answer any questions that the adolescent or parent may have about the study.

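### A single block size of 4, stated in the protocol of an open-label, single-site trial, could let enrolling staff know up to about one allocation in three in advance

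*Combined protocol and SAP*

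**What the plan says.** - **Block size.** Statistical Considerations, item 1: "Participants will be recruited in randomization blocks of 4". No other size is mentioned. The same item names four subgroups, age 12-14 or 15-17 crossed with pump or pen therapy, and aims for at least 10 participants in each. It does not say whether blocks run within those subgroups.
- **Design.** Study Design, item 2: "This is a randomized control, open-label, single-site clinical trial".
- **Ratio.** Not stated in words. Equal allocation is implied by "approximately 40 adolescents & 40 parent(s)/guardian(s) in each arm will complete the study".
- **When staff learn the assignment.** Study Procedures, Main Study, Visit 2: "Adolescent subjects will be randomized and trained on the use of the study CGM and Fitbit". Visits 1 and 2 may be combined. If they are more than 28 days apart, HbA1c is repeated.
- **Primary analysis.** Statistical Considerations, items 2 and 4: parent and adolescent scores on the Family Communication Inventory are summed and compared between arms by t-test. Multivariable ANOVA is a secondary analysis.
- **Not described.** A central or sealed allocation system, varied block sizes, or withholding the block size from those who enrol.

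**The concern.** In an open-label trial at one site, the team that enrols the next dyad can see how earlier dyads were allocated. If the team also knows that every four consecutive allocations contain two of each arm, part of the list can be worked out. Concealing the list does not prevent this, because the deduction uses only past assignments and the block size.

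Someone who knows the next arm could, even without intending to, hurry or delay a dyad that seems likely to engage well. The protocol leaves room for this: the interval between Visits 1 and 2 is flexible, and some exclusions rest on the investigator's judgement. What staff would notice at screening, how readily parent and child talk about diabetes, is close to what the primary score measures. A t-test without baseline adjustment would not correct for selected entry.

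**Working it through.** The plan gives no predictability figure, so there is none to reproduce.

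**Inputs.** Block size 4 (Statistical Considerations, item 1). Two of each arm per block (assumed, from 40 completers per arm). 80 dyads to complete and up to 105 to consent (Human Participants, items 1 and 4). Minimum of 10 per subgroup (item 1). SD 12.5, mean 90.3 and target difference 8.5% (item 2).

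**Step 1: certain allocations in a complete block.** A 2:2 block has 6 equally likely sequences. An allocation is certain once one arm's two places are used up.
- Positions 1 and 2: probability 0.
- Position 3: the first two were the same arm in 2 of 6 sequences, so 1/3.
- Position 4: always, so 1.

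Share = (0 + 0 + 1/3 + 1)/4 = 33.3%. Over 80 dyads in complete blocks that is 80/3 = 26.7 allocations.

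**Step 2: best guess.** Chances of a correct guess at positions 1-4 are 1/2, 2/3, 2/3 and 1. Share = (17/6)/4 = 17/24 = 70.8%, against 50% under simple randomisation.

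**Step 3: incomplete last blocks.** Each complete block has 4/3 certain allocations; the first two places of an unfinished block have none.
- One list of 105: 26 × 4/3 = 34.7, so 34.7/105 = 33.0%.
- Stratum of 26 (about 105/4): 6 × 4/3 = 8, so 8/26 = 30.8%.
- Stratum of 10: 2 × 4/3 = 2.67, so 2.67/10 = 26.7%.

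**Step 4: randomly varied sizes.** Simulation of an observer who knows which sizes are in use and all earlier allocations, but not the order of the sizes, in strata of 20 to 26 dyads (single size of 4: complete blocks):

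| Block sizes | Certain | Best guess correct |
|---|---|---|
| 4 only | 33.3% | 70.8% |
| 4 and 6 | about 6% | about 69% |
| 4, 6 and 8 | about 2% | about 67% |

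**Step 5: what certainty could do to the result (illustration only).** Suppose every certain allocation is acted on, so that dyads entering this way are shifted by d SD in the direction that favours CloudConnect. The shift d is an assumption; the documents give no value. Bias = 2 × share × d × 12.5. The target is 0.085 × 90.3 = 7.7 points. The standard error with 40 per arm is 12.5 × √(2/40) = 2.80.

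| d | Bias, share 33.3% | % of target | Type I error (two-sided 5%) | Type I error, share 5.9% (sizes 4 and 6) |
|---|---|---|---|---|
| 0.1 | 0.8 | 11% | 6% | 5.0% |
| 0.25 | 2.1 | 27% | 12% | 5.2% |
| 0.5 | 4.2 | 54% | 32% | 5.8% |

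Acting on best guesses would add bias under either scheme.

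**The case against.** **Blocks of 4 are conventional for small strata, and varying them changes little on the usual measure.** This stands in part. Best-guess accuracy falls by only two to four points. In a stratum of 10 it is (2 × 17/6 + 1/2 + 2/3)/10 = 68.3% with a single size of 4, against about 68% with sizes 4 and 6. What changes is the certain share.

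**The inputs are partly inferred.** This also stands. That the size is fixed follows only from one size being given. The documents do not say who could read the block size during recruitment, or that blocks run within strata. An unpublished concealment procedure may exist, though it would not stop deduction by someone who knows the block size.

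**There are partial safeguards.** Combining Visits 1 and 2 shortens the window between eligibility and assignment, but it is optional. The communication inventory is also given at baseline, so selection might appear as an imbalance, and ANOVA is foreseen if key variables differ. That analysis is secondary. Baseline questionnaires may also be answered up to a week after the visit, so with combined visits they may follow assignment.

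**Stronger readings that the documents do not support.**
- A reader might infer that selection bias is present. The documents show a route to it, not that anyone used it.
- A reader might infer a conflict of interest from the entry "Other: Center for Diabetes Technology (CDT) personnel" under who generates the scheme, since the team "works in alliance with the Center for Diabetes Technology at the University of Virginia". The tick marks on that list cannot be read, and nothing says that this centre's personnel screen or enrol dyads.
- A reader might count the timing of Visit 2 among discretionary entry criteria. It is not an entry criterion; it is only flexible scheduling. Willingness to take part belongs to the family, not to the investigator.

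**Conclusion.** The point holds as a predictability risk. Up to about one allocation in three could be known in advance: 33.3% in complete blocks, about 31% in strata of 26 and about 27% in strata of 10. This rests on 1:1 allocation, a block size that is always 4, and enrolling staff who know that size and keep a tally (one tally for a single list, four if blocks are stratified). The share does not measure bias; the size of any bias depends on behaviour about which the documents say nothing. The change is worth making because it costs little and the primary comparison has no stated baseline adjustment. It is an inexpensive improvement to the design and does not by itself invalidate the trial.

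**What to change.** 1. Use permuted blocks of randomly varying size (for example 4 and 6, or 4, 6 and 8), and state that they run within the four age-by-therapy strata at 1:1.
2. Remove the block sizes from the protocol and keep them in a restricted randomisation file that those who screen and enrol cannot open.
3. State how allocation is concealed, and release each assignment only after eligibility and consent are recorded.

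Step 3 is needed alongside step 1, because varied sizes still leave about two guesses in three correct. If enrolment has begun, apply the change to the remaining dyads and report the scheme used before it. The cost is a few lines of code, a short protocol edit, and slightly looser within-stratum balance if recruitment stops mid-block.

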The first of two studies associated with this proposal was a needs assessment study that reveals patients' and primary informal caregivers' needs/preferences for the technology core of Cloud Connect (UVA IRB-SBS #2016-0273). This second study will implement, a system that aggregates blood glucose values, exercise, insulin, and meal information collected from individuals with T1D. This information is then analyzed to determine if there are areas of hypo and hyperglycemic risk and how those risk zones may relate to physical activity and insulin dosing behavior. From that analysis, a report is generated and sent to the adolescents and their parents/guardians on a weekly basis giving them insight into how they can increase their ability to control their blood glucose values.

The results of this project will inform the design information technology that improves engagement and clinical outcomes for patients who require continuous monitoring and who engage an informal primary caregiver in self-management outside clinical settings.

Objectives/Hypothesis

The research project proposed here seeks to assess an approach to self-management called CloudConnect, evaluating the impact of CloudConnect on patient engagement, dyad engagement, and clinical outcomes in adolescent T1D.

This assessment will address the essential question of how adolescents and their parent/guardian respond to this new approach to self-management. This study is designed to assess the impact of a T1D-specific CloudConnect implementation on patient engagement, dyad engagement, and clinical outcomes as well as the relationships among these outcome measures for adolescents with diabetes. Throughout this protocol, 'the subject' will refer to the dyad of an adolescent and one parent/guardian.

The randomized controlled trial of CloudConnect is intended to compare the impact of this new model of self-management with use of their personal insulin parameters with the addition of continuous glucose monitoring (CGM) and Fitbit, if not already in use by subject. Assessment between the study subject/parent using validated surveys and assess clinical outcomes including HbA1c, number of hypoglycemic events, etc. over the 3-month period.

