- Medication stability in the preceding two months if taking antihypertensive, thyroid, anti-depressant or lipid lowering medication.

2. List the criteria for exclusion for Pilot and Main Study Adolescent Subjects

- Children outside the ages of 12-17 y.o. or those who do not have a parent/guardian willing to participate
- Diabetic ketoacidosis in the past 6 months
- Pregnancy, breast-feeding, or intention of becoming pregnant
- Current or recent alcohol or drug abuse by patient history
- Mental incapacity, unwillingness or language barriers precluding adequate understanding, cooperation, or ability to fill out questionnaires.
- Any skin condition that prevents sensor placement (e.g., bad sunburn, pre-existing dermatitis, intertrigo, psoriasis, extensive scarring, cellulitis)
- Psychiatric disorders that would interfere with study tasks (e.g. cognitive disability, psychiatric hospitalization within 12 months)
- Use of acetaminophen (*this criteria only applies when the CGM version being used is older than the G6*)
- Use of long-acting insulin that is not Lantus or Tresiba
- For subjects who currently use a close-loop insulin pump and CGM: not being willing to turn off the closed-loop function
- Conditions that would make use of a CGM difficult (e.g., blindness, severe arthritis, immobility)
- Cystic fibrosis

- Current use of oral/inhaled glucocorticoids or other medications, which in the judgment of the investigator would be a contraindication to participation in the study
- Any other comorbidity that at the judgment of the investigator may interfere with the participation on the study (i.e. uncontrolled high blood pressure or thyroid disease, current diabetic microvascular complications, current diagnose of gastroparesis)
- Severe hypoglycemia resulting in seizure or loss of consciousness in the 6 months prior to enrollment
- Use of a device that may pose electromagnetic compatibility issues and/or radiofrequency interference with the Dexcom CGM (implantable cardioverter-defibrillator, electronic pacemaker, neurostimulator, intrathecal pump, and cochlear implants)
- Active enrollment in another clinical trial

No eligibility criteria is required for parent(s)/guardian(s) other than the legal relationship and 18+ yo.

3. List any restrictions on use of other drugs or treatments.

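### Device use at entry (no CGM, CGM, closed loop) is missing from the planned HbA1c and CGM comparisons; fixing it in advance as a covariate is a cheap precision gain

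*Combined protocol and SAP*

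**What the plan says.** - **Strata.** Statistical Considerations, item 1, aims for at least 10 participants in "each of the 4 stratification subgroups based on age (12-14 y.o and 15-17 y.o.) and insulin therapy (CSII and insulin pen"). It adds: "Participants will be recruited in randomization blocks of 4". Prior CGM or closed-loop use is not listed.
- **Analysis.** Item 4 compares the arms on the FCI by t-test and treats the secondary outcomes, including HbA1c and the CGM measures in item 5, the same way. A multivariable ANOVA is a secondary analysis, intended chiefly for cases where important variables turn out to differ between groups. The examples are daily steps and the share of injection users among completers. No list of covariates is fixed.
- **What changes at entry.** Objectives/Hypothesis describes the comparator as the participant's own insulin parameters "with the addition of continuous glucose monitoring (CGM) and Fitbit, if not already in use by subject". One exclusion criterion reads: "For subjects who currently use a close-loop insulin pump and CGM: not being willing to turn off the closed-loop function". Enrolled closed-loop users have therefore accepted switching it off.
- **What the hypothesis says.** The Control Group "will improve management modestly initially (as a result of either of new access to CGM or the Hawthorne effect of being studied"). Its engagement measures "will return to baseline levels by the 12-week evaluation".
- **What is already known about each participant.** Closed-loop use comes up at screening. CGM experience is established at Visit 2: "For subjects who have CGM experience, the investigator will determine if it is appropriate for he or she to skip the run-in period".

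**The concern.** Three kinds of participant enter. Those with no current CGM gain one. Current CGM users without closed loop see little or no change in monitoring. Closed-loop users give up automation. For the first and third kinds, baseline HbA1c reflects a different way of managing glucose from the one used during follow-up. Baseline HbA1c therefore cannot fully stand in for device status, and it may be missing altogether where stay-at-home orders applied. The insulin-therapy stratum does not help, because closed-loop users sit inside the CSII cells with other pump users.

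If device status predicts HbA1c or CGM outcomes, leaving it out keeps that variation in the error term. It also lets a chance difference in device mix move the arm contrast in a trial of about 80 completing dyads. The ANOVA is a weak remedy: it is secondary, its covariates are not fixed in advance, and for participant characteristics the trigger is an imbalance seen among completers.

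**Working it through.** **The plan's own figure.** Inputs from Statistical Considerations, item 2: FCI mean 90.3, SD 12.5, difference 8.5%, power 80%, alpha 0.05 (two-sided assumed), 40 completing dyads per arm.

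- Difference: 0.085 × 90.3 = 7.68 points; 7.68 / 12.5 = 0.614 SD.
- n per arm = 2 × (1.960 + 0.842)² × (12.5 / 7.68)² = 41.6, so 42 against the stated 40.
- Power at 40 per arm: 78.4% by normal approximation, 77.4% by noncentral t. The stated design is reproduced closely.

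**HbA1c change.** The documents give no prevalence, shift or SD, so every input here is an assumption. Let p₁ be the share without CGM, with mean shift s₁; p₂ the closed-loop share, with mean shift s₂; everyone else 0. Take the SD of HbA1c change as 0.8, so the variance is 0.64.

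V = p₁s₁² + p₂s₂² − (p₁s₁ + p₂s₂)²; R² = V / 0.64; sample-size equivalent = 1 / (1 − R²).

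| Case | p₁, s₁ | p₂, s₂ | V | R² | 1/(1 − R²) |
|---|---|---|---|---|---|
| Smallest | 30%, −0.2 | none | 0.0084 | 1.3% | 1.01 |
| Low | 30%, −0.3 | 10%, +0.3 | 0.0324 | 5.1% | 1.05 |
| Central | 40%, −0.4 | 15%, +0.5 | 0.0943 | 14.7% | 1.17 |
| High | 50%, −0.5 | 20%, +0.6 | 0.1801 | 28.1% | 1.39 |

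Central case in full: 0.40 × 0.16 + 0.15 × 0.25 − (−0.16 + 0.075)² = 0.1015 − 0.0072 = 0.0943.

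**What the adjustment costs.** With 80 dyads the t-test has 78 error degrees of freedom. Estimating two more coefficients inflates the variance on average by about 1 + 2/(78 − 2 − 1) = 1.027. A three-level factor therefore has to explain about 1 − 1/1.027 = 2.6% to break even. The smallest case gains nothing. The central case nets 1 / (0.853 × 1.027) = 1.14.

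**Chance imbalance.** At 40 per arm the standard error of the HbA1c contrast is 0.8 × √(2/40) = 0.179. In the central case, device mix contributes an SD of √(2 × 0.0943/40) = 0.069 to that contrast. By simple binomial sampling, a gap of 20 percentage points or more between arms has probability about 7% (prevalence 30% or 70%) to 9% (prevalence 50%). With a shift of −0.4, a 20-point gap moves the contrast by 0.20 × 0.4 = 0.08.

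**FCI.** Treat prior use as a binary factor with assumed prevalence p (30–70%) and user/non-user difference e in SD units. Then R² = p(1 − p)e² and the adjusted SD is 12.5 × √(1 − R²). Normal approximation, 40 per arm, before the small estimation cost above:

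| e | R² | Power |
|---|---|---|
| 0.2 | about 1% | 78.8% |
| 0.5 | 5–6% | 80.5–81.0% |
| 0.8 | 13–16% | 83.9–85.0% |

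Against 78.4%, the gain is roughly 0.3 to 6.6 points.

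**Subgroups and strata.** If 40% have no CGM, there are 16 per arm, and the detectable FCI difference at 80% power is 2.802 × 12.5 × √(2/16) = 12.4 points, or 13.7% of 90.3, against the planned 8.5%. Adding three device levels to the 2 × 2 strata gives 12 cells for about 80 completers, with blocks of 4.

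**The case against.** The case for leaving the plan alone is substantial.

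- Randomisation keeps the arm comparison unbiased, and the t-test's standard error already allows for chance imbalance. This stands.
- The variance shares rest on assumed inputs. The opposite-direction shift for closed-loop users has no source in the documents. This stands, and it is why the range reaches down to about 1%.
- The calculation concerns HbA1c change, whereas the plan does not say whether secondary t-tests use change or final values. With final values, the relevant quantity is how follow-up levels differ by entry status, and that share could be smaller or larger. No pre-entry CGM period is planned either, so no comparable figure can be given for the CGM outcomes. This also stands.
- The secondary ANOVA could admit device status. True, but only as an unlisted covariate chosen after the data are seen. It is a partial safeguard and does not replace a fixed term.
- CGM experience, which governs the run-in, is not current use: a lapsed user also gains a CGM at entry. This is right, and the recorded field should be current use.

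A reader might infer more than the documents support. Entry does not alter glucose management for every participant. Nor does the hypothesis make prior use the driver of early improvement: it offers new CGM access or the Hawthorne effect, for the Control Group, and the latter could touch anyone. It predicts nothing for closed-loop users. It also has Control engagement back at baseline by week 12, around when the final FCI is collected, which gives little reason to expect a large device effect on the primary outcome.

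**Conclusion.** The point holds as a cheap improvement to the HbA1c and CGM analyses. Device status at entry is a plausible predictor that the protocol itself points to. It can be recorded for every participant before randomisation, and the plan uses it in neither the strata nor the main tests. Under the stated assumptions it explains about 1% to 28% of the variance of HbA1c change. The gain therefore runs from nil to worthwhile, and the documents cannot narrow it. For the FCI, the gain of 0.3 to 6.6 power points is small and uncertain.

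Three stronger conclusions might be inferred and should not be. The arm comparison is not biased. There is no shortfall against the stated power on this account: the planning SD of 12.5 comes from people described as eligible, so if they included both CGM users and non-users, that variation is already in it. And the variance is not known; it is assumed.

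**What to change.** - Record current device use at screening, before randomisation, in three levels: no current CGM, current CGM without closed loop, closed loop. Base it on current use, not past experience.
- Pre-specify this factor as a fixed covariate in the HbA1c comparison, together with baseline HbA1c where available, and as a fixed covariate in the CGM comparisons. State that it replaces the imbalance-triggered choice of covariates for these outcomes.
- Treat its inclusion in the FCI model as optional.
- Leave the randomisation strata unchanged. Stratifying alone would not remove the variation from an unadjusted t-test, and it would leave very small cells.
- Show any arm effects within device subgroups as descriptive only.

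The cost is one recorded field and two degrees of freedom. If the factor explains less than about 2.6% of the variance, adjustment brings no gain and a very slight loss. Recruitment, sample size and conduct are unaffected.
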